#### **7.2.4 Multiparametric magnetic resonance imaging (MRI)**

(tbd)

#### **7.2.5 Fusion biopsy system**

(tbd)

### **7.3. Dosages, dosage modifications and method of administration**

#### **7.3.1 Ultrasound contrast agent**

In this study, the recommended dose of 2.4 mL will be used.

Intravenous use

The recommended doses of SonoVue in adults are:

- B-mode imaging of cardiac chambers, at rest or with stress: 2 mL.
- Vascular Doppler imaging: 2.4 mL.

SonoVue should be administered after drawing into the syringe by injection into a peripheral vein. Every injection should be followed by a flush with 5 mL of sodium chloride 9 mg/mL (0.9%) solution for injection.

### **7.4. Preparation and labelling of Non-Investigational Medicinal Product - ultrasound contrast agent**

#### **7.4.1 Preparation**

Pack size: 1 vial + 1 pre-filled syringe + 1 'MiniSpike' rec. device

If SonoVue is not used immediately after reconstitution the dispersion will be shaken again before being drawn up into a syringe. The product is for a single examination only. Any unused liquid remaining at the end of an examination must be discarded.

[figure not shown]

Figure 3: Reconstitution instructions

#### 7.4.2 Reconstitution instructions

The reconstitution instructions below are supported by images in figure 3.

1. Connect the plunger rod by screwing it clockwise into the syringe.
2. Open the MiniSpike transfer system blister and remove syringe tip cap.
3. Open the transfer system cap and connect the syringe to the transfer system by screwing it in clockwise.

4. Remove the protective disk from the vial. Slide the vial into the transparent sleeve of the transfer system and press firmly to lock the vial in place.
5. Empty the contents of the syringe into the vial by pushing on the plunger rod.
6. Shake vigorously for 20 seconds to mix all the contents in the vial to obtain a white milky homogeneous liquid.
7. Invert the system and carefully withdraw SonoVue into the syringe.
8. Unscrew the syringe from the system.

After reconstitution, SonoVue is a homogeneous white milky dispersion. Do not use if the liquid obtained is clear and/or if solid parts of the lyophilisate are seen in the suspension. SonoVue dispersion should be administered within six hours of its preparation. Do not throw away any medicines via wastewater. Ask your pharmacist how to throw away medicines you no longer use. These measures will help protect the environment.

#### **7.4.3        Labelling**

1. Name of the medicinal product: SonoVue 8 microlitres/mL powder and solvent for dispersion for injection sulphur hexafluoride
2. statement of active substance(s): Each mL of the dispersion contains 8  $\mu$ Lsulphur hexafluoride microbubbles, equivalent to 45 micrograms.
3. List of excipients: Macrogol 4000, distearoylphosphatidylcholine, dipalmitoylphosphatidylglycerol sodium, palmitic acid, Solvent: sodium chloride 9 mg/mL
4. Pharmaceutical form and contents: 1 powder vial, 1 pre-filled syringe of solvent, 1 transfer system
5. Method and route(s) of administration: Intravenous or intravesical use. Read the package leaflet before use. For single use only
6. Special warning that the medicinal product must be stored out of the reach and sight of children: Keep out of the sight and reach of children
7. Name and address of the marketing authorization holder: Bracco International B.V., [name], The Netherlands

## 8. METHODS

### 8.1. Study parameters/endpoints

This paragraph describes the study endpoints of the clinical study.

#### 8.1.1 Main study parameter/endpoint

The primary endpoint of this study is clinically significant (GG  $\geq 2$ ) PCa. The detection rate of this endpoint in any core for each biopsy strategy will be assessed to demonstrate the non-inferiority of PCaVision targeted biopsy strategy in comparison with MRI targeted biopsy strategy. The detection rate is expressed with patients as the unit of analysis.

#### 8.1.2 Secondary study parameters/endpoints

- proportion of men in whom targeted biopsies could have been safely omitted in the PCaVision pathway compared to the MRI pathway. This is defined as the number of men in whom no lesions for target biopsies have been identified by PCaVision while no clinically significant cancer is detected in either MRI targeted biopsies or systematic biopsies. The combined findings of all types of biopsies will serve as the reference standard to define 'safe'.
- same diagnostic accuracy analyses as described in the primary endpoint for different definitions of the target condition. This includes: (i) ISUP  $\geq 3$  in any of the biopsy cores taken from a lesion; (ii) ISUP  $\geq 2$  with cribriform growth and/or intraductal carcinoma (CR/IDC) in any of the biopsy cores taken from a lesion; (iii) ISUP = 1.
- comparison of the number of men in whom the PCaVision pathway provided insufficient quality images or targeted biopsies with the number of men with insufficient quality MRI images or target biopsies in the MRI pathway.
- same diagnostic accuracy analysis as described in the primary and secondary outcome but using increased ultrasound image quality requirements (predefined and automated in PCaVision)

### 8.2. Randomisation, blinding and treatment allocation

All patients will undergo both PCaVision and MRI imaging before the scheduled biopsy appointment (fully paired diagnostic accuracy design). The MRI – based biopsy targets and PCaVision - based biopsy targets are appointed independently from, and blinded for each other by 2 specialized readers.

After the imaging has been recorded, 0 to 2 different biopsies procedures are performed:

- (1) a maximum of 6 targeted biopsies in maximum 2 different lesions are taken by one physician, from the MRI lesions delineated by the radiologist. The following biopsy approach is used. When 1 suspicious lesion has been identified, 3 targeted biopsies

will be taken. When 2 lesions have been identified, 3 targeted biopsies will be taken per lesion, so 6 biopsies in total. In case 3 or more suspicious lesions have been found, 2 lesions will be selected based on: (1) PI-RADS and (2) size. Consecutively, 3 targeted biopsies will be taken from these 2 selected lesions. So, the maximum number of targeted biopsies per imaging technique is 6. The physician is blinded for the PCaVision results. When there are no suspicious lesions identified on MRI, this biopsy will not be performed.

(2) a maximum of 6 targeted biopsies in maximum 2 different lesions are also taken by this same physician from the lesions identified on PCaVision by the CEUS expert. The same biopsy approach as for MRI is used. When 1 suspicious lesion has been identified, 3 targeted biopsies will be taken. When 2 lesions have been identified, 3 targeted biopsies will be taken per lesion, so 6 biopsies in total. In case 3 or more suspicious lesions have been found, 2 lesions will be selected based on: (1) severity indication and (2) size. Consecutively, 3 targeted biopsies will be taken from these 2 selected lesions. So, the maximum number of targeted biopsies per imaging technique is 6. The physician is blinded for the MRI results and the systematic biopsy approach and outcomes. When there are no suspicious lesions identified on PCaVision, this biopsy will not be performed.

When suspicious lesions have been identified on both PCaVision and MRI, the targeted biopsy procedures are performed in a randomized order by applying block randomization (with block sizes varying between 6 and 10) using a computer-generated list, to prevent potential bias by post-biopsy haemorrhage.

Due to the nature of the image fusion which is recognisable for both pathways (MRI vs PCaVision), the physician performing the targeted biopsies cannot be blinded for the image modality on which the suspected lesions were identified.

The pathologists interpreting the biopsies (targeted and systematic if available) will be blinded to which modality the target biopsies are based on (PCaVision and MRI results).

### **8.3. Study procedures**

#### **8.3.1      Prostate magnetic resonance imaging (MRI)**

MRI will be performed in supine position on a 3 Tesla MRI. Pre-biopsy prostate MRI image acquisition will be performed according to the most recent Prostate Imaging Reporting And Data System (PI-RADS) guidelines [33]. MRI sequences will include at least T1-weighted, T2-weighted, Diffusion-weighted imaging (DWI) and calculation of apparent diffusion coefficient (ADC) maps.

MRI will be evaluated by a adequately trained uro-radiologist with prostate MRI experience (blinded for 3D mpUS results) on prostate volume and area's suspicious for PCa. Scoring of suspicion will be performed using the European Society of Urogenital Radiology (ESUR) PI-

RADS standardized scoring system [33]. All lesions will be marked and delineated for MRI-TRUS fusion.3D multiparametric ultrasound (mpUS).

### **8.3.2 3D multiparametric ultrasound (mpUS)**

The procedure of 3D multiparametric ultrasound consists of 3 components: (1) intravenous administration of ultrasound contrast; (2) rectal multiparametric ultrasound imaging; (3) PCaVision: artificial intelligence algorithm analyzing the images.

#### *Ad 1. Intravenous administration of ultrasound contrast*

All patients will undergo 3D multiparametric ultrasound imaging before or during the targeted biopsy that is scheduled. To be able to carry out 3D multiparametric ultrasound, intravenous administration of an ultrasound contrast agent must be carried out. SonoVue® (sulphur hexafluoride, Bracco Imaging S.p.A., Colleretto Graciosa, Italy) will be used as the ultrasound contrast agent in this study. This is an additional procedure for patients participating in the study. In usual care, transrectal ultrasound examination is without contrast. SonoVue® is a registered product used in various ultrasound examinations of the heart, vasculature and of the excretory urinary tract. Details of this product and its usage can be found in Chapter 7.

In the procedure, an endorectal TRUS probe will be placed in the rectal cavity of the patient. Consecutively patients will undergo: 3D Doppler, 3D-SWE, 3D-B-mode and 4D-CEUS. For 4D-CEUS one 2.4mL bolus of SonoVue® will be administered intravenously. A two-minute recording in the contrast enhanced mode will be made following the administration of SonoVue®. The entire 3D mpUS imaging protocol will take approximately 10 minutes.

#### *Ad 2. Transrectal ultrasound imaging*

The clinically approved ultrasound system LOGIQ™ E10 (GE Healthcare, Milwaukee, WI, USA) consisting of all necessary requirements will be used for the purpose of this study. Three-dimensional (3D) prostate CEUS recordings will be captured including 3D CUDI with the 2.4 mL bolus injection of SonoVue® (Bracco, Geneva, Switzerland).

#### *Ad 3. PCaVision*

The 3D multiparametric ultrasound images will be stored and transported to an image processing system for 3D multiparametric ultrasound analysis. The CEUS recordings will be subjected to PCaVision quantification analyses based on the pharmacokinetic modelling of the contrast bolus transport through the microvasculature of the prostate as a convective-dispersion process. A PCaVision parametric map will be generated. So, different analyses will be done for each modality (B-mode, CEUS, SWE) with the 3D multiparametric ultrasound classifier parametric image map as end result.

A training consisting of at least 3-5 patients will be performed under supervision of an expert teacher for each investigator in each participating center to optimize the protocol, local

procedures, and preparation prior to the start of the study. The obtained results from these patients will be incorporated in the final statistical analysis and are normal part of the study. The training will be divided into 2 parts: 1) performance of the PCaVision examination 2) interpretation of the PCaVision examination. During this training period, the expert teacher will be on-site in each center to monitor study procedures, identify problems, and provide direct feedback where possible and needed. The expert teacher will ensure sufficient quality of the obtained results by the learners, and finally certify the learners. Training records will be maintained to document the training of the staff.

A total of 50 patients will be asked to undergo an additional ultrasound scan in the same session, as detailed in Appendix I.

### **8.3.3 Biopsy procedure and histological examination**

An urologist will perform software-assisted fusion TBx or cognitive TBx based on the standard of care of each participating centre. For each imaging modality (e.g. MRI and 3D mpUS), a maximum of 2 lesion will be targeted. Each lesion will be sampled using 3 biopsy cores. In case both imaging techniques have identified lesions to be biopsied, the targeted biopsy procedures are performed in a randomized order to prevent potential bias.

The applied prostate biopsy method; transperineal will be selected based on the standard of care of each participating clinical centre.

Individual biopsy cores from targeted biopsies will be separately analysed by an uropathologist for the presence of PCa, ISUP, Gleason score (GS), percentage tumour core involvement and morphological patterns including cribriform growth pattern and intraductal carcinoma (CR/IDC) in accordance with the 2019 ISUP guidelines [34]. A work order instruction for the exact sample labelling of the biopsies and histopathological workup will be provided and agreed on with each clinical site.

### **8.4. Withdrawal of individual subjects**

Subjects can leave the study at any time for any reason if they wish to do so without any consequences. The investigator can decide to withdraw a subject from the study for urgent medical reasons. Furthermore, when subjects experience poor diagnostic imaging or other technical issues related to US, MRI or biopsy, they will be excluded for analysis.

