#### **4.5. Sample size calculation**

The sample size calculation is based on demonstrating non-inferiority between the detection rate of clinically significant cancer from the PCaVision pathway and the MRI pathway using patients as the unit of analysis and data from the fully paired design.

The detection rates of PCa (GG $\geq$ 2) based on MRI and PCaVision targeted biopsies are expected to be around 30%. These values are based on the detection rates of PCa (GG $\geq$ 2) reported by Mannaerts et al., 2020 [30] and Grey et al., 2022 [43], which were found to be 29% and 30% with MRI and 28% and 26% with 2D CUDI (older version of PCaVision), respectively.

The non-inferiority margin is set to 5% absolute difference in detection rate. The expected proportion of discordant pairs is 10%. This proportion expresses the degree in which PCaVision and MRI disagree with respect to detecting and missing significant cancers in a paired design. This parameter is relevant when analysing data from a paired study design. A smaller percentage of discordant pairs will lower the required sample size. In the studies of Mannaerts et al., 2020 [30] and Grey et al., 2022 [43], the percentage discordant pairs were 10.1% and 8.9%, respectively.

Our assumptions of the sample size calculations are therefore the following: an expected detection rate of 30% for both imaging techniques, a non-inferiority margin of 5% points and a percentage discordance between both imaging techniques of 10%, a one-sided type 1 error of 2.5% (as recommended by the European Medicines Agency) and a power of 80%. This leads to a required total sample size of 350 patients.. This is the total number of men who need to undergo both PCaVision and MRI, and produce images of sufficient quality, followed by targeted biopsies if indicated. This sample size calculation was performed according to Liu et al., 2002 [47] and Hintze, 2008 [48].

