With both imaging pathways, we expect a certain percentage of men in whom either PCaVision or MRI or both produce image quality that is insufficient to perform targeted biopsies upon, or technical issues when performing targeted biopsies. The primary, paired analyses will be based on men having sufficient quality images and targeted biopsies from both imaging techniques. During the development of the PCaVision algorithm, insufficient scans were manually excluded to ensure optimal quality for training purposes. Currently, PCaVision incorporates an automated image quality check to guarantee sufficient signal and quality. To compensate for discarded scans due to quality issues, 25% additional patients will be included. The total sample size will therefore be 438 subjects to obtain 350 evaluable patients in the paired analysis.

As we would like to include PCa patients from 5 clinical centres, the patient number target per centre is 80, with a range of 40-120.

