### **8.5. Replacement of individual subjects after withdrawal**

Subjects will be replaced after the withdrawal.

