### 10.1. Primary study endpoint analysis

The main analysis is the comparison of the detection rate of clinically significant cancer (defined as GG $\geq$ 2) between the PCaVision targeted biopsy pathway and the MRI targeted pathway. We will calculate the difference in these detection rates and its corresponding 97.5% confidence interval. Because of the paired design of our study, we will use the approach of Liu which accounts for the correlation between the detection rates of both pathways [44,45,46]. A one-sided 2.5% equivalence test will be performed to formally evaluate whether the lower bound of the confidence interval will not exceed the non-inferiority margin specified at an absolute difference in detection rates of 5%.

As a secondary analysis, the comparison of the proportion of men in whom targeted biopsies could have been safely omitted in the PCaVision pathway compared to the MRI pathway.

This ~~10.2. Secondary study endpoint analysis~~ with respect to detection rate (see above) does not come at the price of fewer patients in whom targeted biopsies can be prevented (e.g., more unnecessary targeted biopsies). For PCaVision this proportion is the number of men in whom there are no lesions to be biopsied based on PCaVision while the MRI biopsy strategy and systematic biopsy (when performed) did not detect clinically significant cancer divided by the total number of men in the study. Likewise, this proportion for MRI is defined as the number of men in whom there are no lesions to be biopsied based on MRI while the PCaVision biopsy strategy and systematic biopsy (when performed) did not

detect clinically significant cancer divided by the total number of men in the study. Given the fully paired nature of the design, the proportions will be tested for being statistically significance different using the McNemar test (two-sided alpha of 5%). The approach of Liu which accounts for the correlation [44,45,46] will be used to calculate a 95% confidence interval for the difference between these proportions.

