Furthermore, the same effect measures and statistical approach will be used as in the previous analyses, only the definition of the target condition will change. The following alternative definitions of the target condition (rather than  $ISUP \geq 2$ ) will be used: (i)  $ISUP \geq 3$ ; (ii)  $ISUP \geq 1$ ; (iii)  $ISUP = 1$ . The reason also assessing alternative definitions is that there is still ongoing discussion about the clinical relevance of these histological findings.

Both imaging techniques (PCaVision and MRI) can produce images of insufficient quality impeding the process of taking targeted biopsies. This hampers the clinical usefulness of the imaging technique in practice. Therefore, we will compare the proportion of men in whom the PCaVision pathway produces insufficient-quality images or targeted biopsies with the proportion of men with insufficient-quality MRI images or target biopsies in the MRI pathway. The same statistical approach for paired proportions will be used in the comparison of the detection rate.

The PCaVision software includes automated detection of ultrasound image quality by analysing patient motion and CEUS signal. We will analyse diagnostic accuracy of PCaVision using the same statistical approach with increased requirements of ultrasound images quality with regards to motion and CEUS signal. The exact levels of these increased requirements are described in section 6.1.2.

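### Section 8.4 excludes men with failed imaging or biopsy from analysis without naming a dataset, which contradicts the image-failure endpoint and leaves replacement of these men unclear

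*Combined protocol and SAP*

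**What the plan says.** **Exclusion.** Section 8.4, headed as withdrawal of subjects, says that "when subjects experience poor diagnostic imaging or other technical issues related to US, MRI or biopsy, they will be excluded for analysis". It does not refer to either dataset of Section 10 or to the quality thresholds of Section 6.1.2.

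**Replacement.** Section 8.5 is one sentence: "Subjects will be replaced after the withdrawal". It has no exception and no cap.

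**Sample size.** Section 4.5 derives 350 evaluable men and then, to cover discarded scans, says that "25% additional patients will be included", giving 438. The second paragraph of Section 10.3 adds a review at half the sample that looks at the frequency of discarded scans and can only raise the total.

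**Datasets.** Section 10 defines a Total study population (all included men) and a Paired dataset (sufficient images and subsequent targeted biopsies for both techniques). It assigns the second to the accuracy comparisons and gives the first no explicit use.

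**Endpoints that need the failed men.** In the secondary analysis (Section 10.2), "we will compare the proportion of men in whom the PCaVision pathway produces insufficient-quality images or targeted biopsies" with the same proportion for MRI, by the paired method used for the detection rate. Safe omission is a count "divided by the total number of men in the study". The failure comparison is also listed in the Summary and Section 2 (images only) and in Section 8.1.2 (images or biopsies).

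**The concern.** A rule that removes men with failed imaging or biopsy from analysis cannot stand beside an endpoint that counts them. Section 10.2 itself says that poor images limit a technique's usefulness in practice. Because the primary analysis is restricted to men with usable data from both techniques, this secondary endpoint is where usability failures become visible. If the dataset is chosen only at analysis, the choice affects how favourable PCaVision looks.

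The second issue is recruitment. The same loss is addressed by the 25% in 4.5, by the upward adjustment in 10.3 and, on one reading, by replacement under 8.5. The plan does not say how these fit together.

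**Working it through.** **1. The plan's own figures.** Inputs from Section 4.5: one-sided alpha 2.5%, power 80%, "an expected detection rate of 30% for both imaging techniques", a margin of 5 points and 10% discordant pairs (5% each way, given equal rates). The paired score-test formula is

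n = [z(0.975)·√v0 + z(0.80)·√v1]² / margin²

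with v1 = 0.10, and v0 = 0.1164 from the restricted estimate at a difference of −5 points.

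n = [1.960 × 0.3412 + 0.842 × 0.3162]² / 0.0025 = 349.6, so 350.

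Inflation: 350 × 1.25 = 437.5, so 438. Both figures reproduce.

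**2. The loss that 438 allows for.** 438 − 350 = 88 men, and 88/438 = 20.1%. This is the loss implied by the buffer, not a forecast that the plan states.

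**3. The failure comparison on each dataset.** Let b be men failing on PCaVision only, c on MRI only and d on both. The difference in failure proportions is (b − c)/n.

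- Paired dataset: men enter only if both techniques succeeded, so b = c = d = 0 and the comparison is 0 versus 0 whatever happened in the trial.
- Total study population: at the loss in step 2, b + c + d = 88 and n = 438. The difference can lie anywhere from −20.1 to +20.1 percentage points, depending on which technique failed.
- Section 8.4 taken literally: the failed men leave every analysis, and the result is again 0 versus 0.

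Section 10.2 names neither dataset. Its reference to the detection-rate approach points towards the Paired dataset; its purpose points towards the Total study population.

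**4. Safe omission.** The stated denominator is all men in the study (438 as planned). With 8.4 applied, it is the evaluable men (350). As an illustration only, 100 safely omitted men would be 100/438 = 22.8% or 100/350 = 28.6%. There is also a numerator gap. Under Section 6.1.2, PCaVision does not process a scan that fails its criteria, so it marks no lesion. The definition does not say whether such a man counts as having no lesion.

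**5. Replacement on top of the buffer.** The failure rates here are assumptions.

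| Reading | 20% failure | 25% failure |
|---|---|---|
| 438 enrolled, failures not replaced | 438 × 0.80 = 350 evaluable | 438 × 0.75 = 328 evaluable |
| Failures replaced until 438 are evaluable | 438/0.80 = 548 enrolled | 438/0.75 = 584 enrolled |

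Exact score-test power is about 81% at 350 evaluable, 79% at 328 and 89% at 438. Replacing men only until 350 are evaluable gives 350/0.80 = 437.5, about 438 enrolled at 20% failure, with no double count.

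**The case against.** The strongest reply is that 8.4 is loose shorthand for the exclusion from the Paired dataset. Section 4.5 ties the quality requirement to the primary, paired analyses. Section 10 defines a population of all included men. The failure comparison is prespecified in several places, with its reason given. Section 12.1.1 requires a case report form for every included subject, and 10.3 reviews discarded scans. This stands as evidence of intent: the sponsor evidently means to count failures. A reader might infer that the endpoint is already emptied, or that replacement hides the failures. The documents do not support either inference, because failures are recorded and the endpoint is lost only if one general sentence overrides Section 10. But intent does not settle the text. Section 10 gives the Total study population no named use, and 10.2 names no dataset.

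On replacement, 8.4 separates men who leave, men whom the investigator withdraws and men excluded from analysis; 8.5 speaks of withdrawal. Only the heading connects the third group to replacement, so double compensation is a possible reading and no more. A reader might also infer that the trial will enrol about 548 men, some 110 more than planned (548 − 438). That requires replacement until 438 men are evaluable, which no section states; 4.5 aims at 350. Nor was 438 a ceiling, since 10.3 already allows an increase.

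**Conclusion.** Wrong as written, as an internal contradiction of modest severity. Section 8.4 taken literally conflicts with the Total study population, with the image-failure endpoint and with the safe-omission denominator. On the Paired dataset the failure comparison is uninformative by construction. The group with no defined place is up to 88 of 438 men, if the loss equals the one the buffer allows for.

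Whether the same loss is compensated more than once is unclear, not established. If it were, the consequence would be over-enrolment with power of about 89%, not a loss of power. The 350 and the 438 are correct. The primary comparison is unaffected, because 4.5 and 10 restrict it to the Paired dataset regardless of 8.4.

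**What to change.** 1. **Section 8.4:** say that men with poor imaging or technical problems are *excluded from the paired dataset only and remain in the total study population*.
2. **Section 10.2:** name the Total study population for the image-failure comparison. For safe omission, name one denominator and state that a failed scan does not count as a finding of no lesions. If the denominator is the Total study population, a man with a failed scan is then counted as not safely omitted for that technique, which also settles his place in the McNemar pairs.
3. **Section 8.5:** state that men with image or technical failures covered by the 25% in 4.5 are not additionally replaced, apart from any increase under the re-estimation in 10.3.

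The cost is a few sentences and no new data. The reported failure rate may be less favourable to PCaVision. The change should be made before the data are analysed, because the choice of denominator affects the result.
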